4.2.2.1. Key Inclusion/Exclusion Criteria

Type	Category	Criteria
Inclusion	5.1.2. Type of Participant and Disease Characteristics	
1. Participants who have a positive SARS-CoV-2 test result within 7 days of randomization (by any validated diagnostic test e.g. RT-PCR, antigen based testing on any specimen type)
 
4. Participant to be dosed less than or equal to 7 days from onset of symptoms to dosing day (D1) Note: Participants will only be excluded if ≥ 9 days since dosing.

Exclusion	5.2.1. Medical Conditions	
1. Currently hospitalized or judged by the investigator as likely to require hospitalization in the next 24 hours Note: Participants will only be excluded if hospitalized at baseline per eCRF form.

	5.2.2. Prior/Concurrent Clinical Study Experience	
5. Enrollment in any investigational vaccine study within the last 180 days or any other investigational drug study within 30 days prior to Day 1 or within 5 half-lives of the investigational compound, whichever is longer

		6. Enrollment in any trial of an investigational drug, vaccine or device study for SARS-CoV-2/COVID-19 within 90 days prior to Day 1 or within 5 half-lives of the investigational compound, whichever is longer
5.2.3. Other Exclusions		7. Immunocompetent individuals who are fully vaccinated against SARS-CoV-2. A person is considered fully vaccinated if at least 14 days have passed since receiving the final dose in a COVID-19 vaccine series. 8. Receipt of convalescent plasma from a recovered COVID-19 patient or anti-SARS-CoV-2 mAb within the last 3 months.

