- Population: All participants in the Intent-to-Treat (ITT) analysis set excluding participants who did not meet key inclusion/exclusion criteria (see section 4.2.2.1).
- Endpoint: Progression of COVID-19 through Day 29 as defined by hospitalization > 24 hours for acute management of illness due to any cause or death
- Summary measure: Absolute difference in the proportion of participants meeting the primary endpoint
- The anticipated intercurrent events are:
 - Not receiving randomized treatment or an alternative study treatment (i.e. treatment misallocation)
 - Discontinuation of study intervention as described in Protocol Section 7.1.
 - Use of medication not permitted during the study as listed in Protocol Section 6.8.1 up to Day 29

All intercurrent events will be handled using a hypothetical strategy where data collected after the occurrence of an intercurrent event will be excluded from the analysis, i.e. assuming the intercurrent event had not occurred.

Rationale for estimand: A hypothetical estimand is used as this is considered more conservative than treatment policy and therefore more appropriate for a non-inferiority comparison.

Supplementary Estimand for the Primary Endpoint

A supplementary estimand will be conducted based on all participants in the ITT analysis set by handling all intercurrent events with a treatment policy strategy (i.e. regardless of the intercurrent events occurring), with all the other attributes being the same as in the primary estimand. To estimate this estimand, all data collected in the ITT analysis set up to Day 29 will be included in the analysis.

[figure not shown]
[figure not shown]
Estimands for Key Secondary Endpoints

The estimand for the secondary endpoint 'Mean area under the curve of SARS-CoV-2 viral load in nasal secretions as measured by qRT-PCR from Day 1 to Day 8 (AUC_{D1-8})' is described by the following attributes:

- Population: All participants in the Virology analysis set, as defined in Section 3
- Summary measure: Treatment ratio (IM/IV) of mean \log_{10} AUC_{D1-8}
- Intercurrent events: Death and use of medication not permitted during the study as listed in Protocol Section 6.8.1 up to day 8
 - Strategy for Death: Composite strategy, where for participants who die prior to Day 8, the AUC_{D1-8} viral load value will be imputed using the worst AUC_{D1-8} viral load value from other participants in the same treatment arm.

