3. ANALYSIS SETS

Analysis Set	Definition / Criteria	Analyses Evaluated
Screened	All participants who were screened for eligibility	Study Population
Enrolled	All participants who entered the study Note screening failures (who never passed screening even if rescreened) are excluded from the Enrolled analysis set as they did not enter the study	Study Population
Randomized	All participants who were randomized. Participants will be analyzed according to the route of administration and dose level they were randomized to: sotrovimab IM (500 mg), sotrovimab IM (250 mg) or sotrovimab IV (500 mg).	Study Population
Intent-to-Treat (ITT)	All participants who were randomized. Participants who were randomized under Protocol Amendment Version 1 and were immunocompetent and fully vaccinated at randomisation will be excluded. Participants will be analyzed according to the route of administration and dose level they were randomized to: sotrovimab IM (500 mg), sotrovimab IM (250 mg) or sotrovimab IV (500 mg).	Study Population Efficacy
Safety	All randomized participants who are exposed to study intervention. Participants will be analyzed according to the route of administration and dose level they actually received: sotrovimab IM (500 mg), sotrovimab IM (250 mg) or sotrovimab IV (500 mg).	Study Population Safety
Pharmacokinetic (PK)	All participants in the Safety analysis set who had at least 1 non-missing PK assessment (Non-quantifiable [NQ] values will be considered as non-missing values). Participants will be analyzed according to the route of administration and dose level they actually received.	PK

Analysis Set	Definition / Criteria	Analyses Evaluated
Virology	
All participants in the ITT analysis set with a lab confirmed quantifiable baseline nasopharyngeal swab at Day 1.
 
Participants will be analyzed according to the route of administration and dose level they were randomized to: sotrovimab IM (500 mg), sotrovimab IM (250 mg) or sotrovimab IV (500 mg).
 
This will be the primary analysis set for virology.
	Efficacy (Virology)

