4.1.2. Baseline Definition

For all endpoints the baseline value will be the latest pre-dose assessment with a non-missing value, including those from unscheduled visits and the screening visit. If time is not collected, Day 1 assessments are assumed to be taken prior to first dose and used as baseline. For endpoints assessed using an analysis set other than the Safety analysis set, the baseline value for subjects who are randomised and not dosed will be the latest assessment with nominal visit on or prior to Day 1.

Unless otherwise stated, if baseline data is missing no derivation will be performed and baseline will be set to missing.

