4.2.2. Main analytical approach

The primary analysis will be conducted on the ITT analysis set, excluding participants who did not meet key inclusion/exclusion criteria (see section 4.2.2.1). All intercurrent events (see below) will be handled using a hypothetical strategy for the primary estimand, i.e. assuming the intercurrent event had not occurred.

The primary endpoint will be summarized using counts and percentages of the number of participants who have progression of COVID-19. The proportion of participants meeting the primary endpoint will be compared for sotrovimab 500 mg IM vs sotrovimab 500 mg IV using a 3.5% non-inferiority margin on the risk difference scale as per section 2.

The proportion of participants meeting the primary endpoint will be compared between treatments using a generalized linear model (GLM) from the binomial family with identity link, adjusted for treatment group (sotrovimab 500mg IV, sotrovimab 500mg IM), derived age group (<65 years old, ≥65 years old, see Section 6.2.7), and gender (female, male).

The absolute risk difference and associated 95% CI will be computed to test for non-inferiority in hypothesis (1).

Covariates may be removed from the model if it fails to converge as described in section 4.1.1. If the model still does not converge a GLM assuming a normal distribution for the endpoint and with identity link will be used, adjusted for the covariates above. If no events are observed on either treatment arm, the Farrington-Manning test will be used to compare arms.

The anticipated intercurrent events are:

- Not receiving randomized treatment or an alternative study treatment (i.e. treatment misallocation)
- Discontinuation of study intervention as described in Protocol Section 7.1.
- Use of medication not permitted during the study as listed in Protocol Section 6.8.1 up to day 29

Events are only deemed to be intercurrent events if they occur before occurrence of the primary endpoint. Data observed in the period following an intercurrent event (i.e. from the study day following the intercurrent event) will be excluded from the analysis. Data from this period will be assumed “missing at random” (MAR).

For participants that withdraw from the study and do not meet the primary endpoint at the time of withdrawal, data in the post-withdrawal period will also be assumed MAR.

Details of the method for multiple imputation is described in section 6.2.8.

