4.2.3. Additional estimands

A supplementary estimand will be conducted in the ITT analysis set by handling all intercurrent events with a treatment policy strategy (i.e. regardless of the intercurrent events occurring), with all the other attributes being the same as in the primary estimand. To estimate this estimand, all data collected in the population of interest up to Day 29 will be included in the analysis. Missing data due to participant withdrawal from study will be handled in the same manner as the primary estimand.

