6.2.4. Study Day and Reference Dates

The safety reference date is the study treatment start date and will be used to calculate study day for all safety measures.

For efficacy, measurements of progressions including: all Hospitalizations, Oxygen Supplementation, and Death will measure from treatment start date to align with safety measurements. Efficacy measurements of all-cause mortality and incidence & duration of ICU, Hospitalization, and Ventilation will calculate study day from date of randomization.

- Ref Date = Missing \rightarrow Study Day = Missing
- Ref Date $<$ First Dose Date \rightarrow Study Day = Ref Date – First Dose Date
- Ref Data \geq First Dose Date \rightarrow Study Day = Ref Date – (First Dose Date) + 1

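### The note on late dosing in SAP 4.2.2.1 counts days from dosing, not from symptom onset to dosing; separately, SAP 6.2.4 gives undosed participants no progression study day (both minor)

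*SAP*

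**What the plan says.** **Late-dosing note.** SAP 1.1 defines the primary-estimand population as "All participants in the Intent-to-Treat (ITT) analysis set excluding participants who did not meet key inclusion/exclusion criteria (see section 4.2.2.1"), and SAP 4.2.2 repeats this. In the table in 4.2.2.1, criterion 4 requires dosing within 7 days of symptom onset. Protocol 5.1.2 has the same criterion, numbered 6 there because the supplied protocol is a later amendment than the one the SAP follows. The note attached to it says "Participants will only be excluded if ≥ 9 days since dosing".

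**Study day.** SAP section 3 defines ITT as "All participants who were randomized. Participants who were randomized under Protocol Amendment Version 1" and then carves out one vaccinated subgroup; it does not require exposure. Undosed participants are foreseen: SAP 4.1.2 says "the baseline value for subjects who are randomised and not dosed will be the latest assessment with nominal visit on or prior to Day 1", and the partial-date rules in 6.2.7 have a branch for participants who never started treatment. For progression, SAP 6.2.4 says "measurements of progressions including: all Hospitalizations, Oxygen Supplementation, and Death will measure from treatment start date to align with safety measurements". Its formulas subtract First Dose Date, and their only missing-value branch is for a missing event date. The next sentence of 6.2.4 uses the randomization date for all-cause mortality and for incidence and duration of ICU stay, hospitalization and ventilation.

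**Estimands.** SAP 4.2.2 lists "Not receiving randomized treatment or an alternative study treatment (i.e. treatment misallocation") as an intercurrent event, and adds "Events are only deemed to be intercurrent events if they occur before occurrence of the primary endpoint". For the supplementary treatment-policy estimand, SAP 4.2.3 says "all data collected in the population of interest up to Day 29 will be included in the analysis".

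**The concern.** The note and its criterion measure different things. The criterion looks back from dosing to symptom onset; the note looks forward from dosing. Because the table decides who is in the primary non-inferiority analysis, a programmer has to reinterpret the note before applying it, and a reader of the report cannot tell from the SAP what was done.

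The second gap concerns participants who were randomized and never dosed. The treatment-policy estimand must count their hospitalizations and deaths up to Day 29, but the progression rule in 6.2.4 has no Day 1 for them. What is at stake is reproducibility of the supplementary analysis. In the primary estimand, data after non-receipt are excluded and imputed, so the gap there is limited to the day assigned to that intercurrent event, including its order relative to any progression in an undosed participant.

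**Working it through.** **1. The note, literal and intended.** Let *k* be the days from onset to dosing and *t* the days elapsed since dosing.

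- Criterion 4: met if *k* ≤ 7.
- Note, literal: exclude if *t* ≥ 9. At dosing *t* = 0, so no one is excluded. By 6.2.4, study day = *t* + 1, so *t* = 9 falls on Day 10 and at Day 29 *t* = 28. Every dosed participant followed to Day 10 or later would be excluded. Neither result is a usable population.
- Note, intended: exclude if *k* ≥ 9. Then *k* ≤ 7 meets the criterion, *k* = 8 is a tolerated deviation, and *k* ≥ 9 is removed. This is the only reading that can operate as a relaxation of the criterion.

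**2. Progression study day.** On or after the first dose, 6.2.4 gives

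study day = event date − First Dose Date + 1.

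| Participant | First Dose Date | Progression study day |
|---|---|---|
| ITT, dosed | present | defined |
| ITT, never dosed | absent | not defined; no branch |

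The randomization origin in the following sentence covers neighbouring endpoints, not progression. The slotting of hospitalization to clinic visits in SAP 4.1.1 serves by-visit summaries and does not date a single event against Day 29.

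**3. Scale, as context only.** The plan's sample size reproduces. With 2% in both arms, a 3.5-point margin, one-sided 2.5% and 90% power (SAP section 5),

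n = (1.960 + 1.282)² × 2 × 0.02 × 0.98 / 0.035² = 336.2, so 337 per arm against the stated 340; power at 340 is 90.3%.

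The protocol synopsis reports 2.7% (IM 500 mg) and 1.3% (IV), with an adjusted 95% CI of −1.24% to 3.45%. Distance to the margin: 3.5 − 3.45 = 0.05 points. Analysed arm sizes are not given, so 300 to 400 per arm is assumed. Unadjusted upper limit = 100 × [p_IM − p_IV + 1.96 × √(p_IM(1 − p_IM)/n_IM + p_IV(1 − p_IV)/n_IV)], with the reported rates rounded to whole events:

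| N per arm | Events IM, IV | Change if one IV event leaves | Change if one IM event leaves |
|---|---|---|---|
| 300 | 8, 4 | +0.24 | −0.41 |
| 340 | 9, 4 | +0.21 | −0.36 |
| 375 | 10, 5 | +0.20 | −0.32 |
| 400 | 11, 5 | +0.19 | −0.30 |

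Removing one participant without progression moves the limit by less than 0.02. Only the changes are used, because the reported estimate is adjusted. They describe how sensitive the limit is to any one participant with progression; they are not an effect of the wording error.

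**The case against.** The strongest reply is that the note is a slip with one workable reading. It shares a cell with the onset-to-dosing criterion, the cutoff of 9 is explicit, and the word *only* shows that the tolerance is deliberate. No one could run the literal version, so two competing populations do not arise. This stands, and it is why the point is minor.

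Three stronger readings are tempting, and the documents do not support them:

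- *A reader might infer that the error puts the non-inferiority result in doubt because the limit is 0.05 points from the margin.* Under the recoverable reading the error changes no one's status, and that distance would make any data rule in this trial look critical. The synopsis also does not name the estimand behind the interval.
- *A reader might infer that the note leaves it open whether never-dosed participants are in the primary population.* Non-receipt is an intercurrent event within that population, so they are implied to be in it, and a participant without an onset-to-dosing interval cannot meet an exclusion based on one.
- *A reader might infer that the SAP has no date origin at all for hospitalizations and deaths of the undosed.* It has one, randomization, for mortality and hospitalization incidence. It does not extend it to progression.

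Two further replies also carry weight. SAP section 1 defers data-handling conventions to an Output and Programming Specification that is not among the documents, so the missing line may exist there. And the choice of Day 1 would matter only for an undosed participant whose event falls near the Day 29 boundary.

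**Conclusion.** Both parts hold, and both are minor. The late-dosing note is wrong as written and should be corrected because it is an operative threshold for the primary population, although its meaning is recoverable. The study-day gap is real in the SAP text and matters mainly for the supplementary treatment-policy estimand.

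The numbers never dosed, dosed 8 days after onset, or excluded at 9 or more days are not in the documents, so no effect on the reported result is shown. The conclusion on study day is that the rule is absent from the SAP, not that none exists. The review takes no position on the 7-day entry criterion or on tolerating day 8.

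**What to change.** 1. Reword the note in SAP 4.2.2.1 so that participants are excluded only if 9 or more days passed from symptom onset to dosing.
2. Add one line to SAP 6.2.4: for ITT participants who were never dosed, Day 1 of the progression endpoints is the randomization date. Dosed participants keep treatment start. If the Output and Programming Specification already holds a rule, cite it instead.
3. Because Day 29 results are already reported, state in the study report how both rules were applied. Give, per arm, the numbers never dosed, dosed at 8 days, and excluded at 9 or more days, with how many of each progressed.

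The cost is one corrected note, one added line and a few counts. No study day changes for any dosed participant, and the design, margin and sample size are untouched.

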4.2.3. Additional estimands

A supplementary estimand will be conducted in the ITT analysis set by handling all intercurrent events with a treatment policy strategy (i.e. regardless of the intercurrent events occurring), with all the other attributes being the same as in the primary estimand. To estimate this estimand, all data collected in the population of interest up to Day 29 will be included in the analysis. Missing data due to participant withdrawal from study will be handled in the same manner as the primary estimand.

4.2.4. Sensitivity analyses

To assess the sensitivity of the results to the missing data, a tipping point analyses will be performed for the hypothetical and treatment policy estimands. The underlying response rate among those subjects with missing response status in each arm will be varied ranging between 0 and 1. This analysis will be two-dimensional, i.e. it will allow for assumptions about the assumed response rate (and thus missing outcomes) in the two treatment arms to vary independently. For combinations of the assumed response rates in the arms, the number of additional responders among subjects with missing response will be imputed multiple times by drawing from a binomial distribution. The absolute difference and associated standard error for each imputed dataset will be calculated using the primary analysis model and results combined using Rubin's rules to calculate the risk difference and the 95% CI for the treatment comparison. Results will be presented via a heatmap.

In addition, a summary of the number of COVID-19 progressions through Day 29 (as defined in section 4.2.1) for the hypothetical estimand will be provided for the split by those progressions that occur <3 days and ≥ 3 days post-dose.

4.3. Secondary Endpoints Analyses

The secondary endpoints will be based on the ITT Analysis Set, unless otherwise specified.

4.3.1. Definition of Secondary Endpoints

4.3.1.1. Safety and tolerability

Adverse events analyses including the analysis of adverse events (AEs), serious AEs (SAEs) and other significant AEs will be based on GSK Core Data Standards.

An overview summary of AEs, including counts and percentages of participants with

- any AE
- any SAE
- any AESI

will be provided as outlined in Section 4.5.2. The Safety analysis set will be used.

Since it will not be possible to delineate in a single participant whether the hospitalization is directly related to COVID-19 complications or could be related to VIR-7831 causing more severe disease due to ADE, all hospitalizations regardless of cause will be included in the primary endpoint. However, if a hospitalization or adverse event is related to expected progression, signs, or symptoms of COVID-19 (as detailed in Section 8.4.8 of the Protocol) or if hospitalization is due to elective treatment of a pre-existing condition that did not worsen from baseline as noted in Section 10.3 of the Protocol it will not be considered as an SAE. These events will be collected and reported as SAEs only if the event is more severe than expected for the participant's current clinical status and medical history or if the investigator feels that it is related to study drug.

In addition, a summary of the number and percentage of participants with disease-related events, that is, events related to expected progression, signs, or symptoms of COVID-19, unless more severe than expected for the participant's current clinical status and medical history will be provided. These events will be captured on the disease related event CRF. This data will also be listed.

The following are examples of events NOT meeting the AE definition but will be classed and captured separately as disease progression events in the CRF:

- hypoxemia due to COVID-19 requiring supplemental oxygen
- hypoxemia due to COVID-19 requiring non-invasive ventilation or high flow oxygen devices
- respiratory failure due to COVID-19 requiring invasive mechanical ventilation or ECMO

4.3.1.2. Immunogenicity of VIR-7831

The incidence and titers (if applicable) of serum ADA to VIR-7831 will be listed and summarized for the Week 36 safety summary in the Safety analysis set.

Additional immunologic analyses may be conducted and will be documented in a separate technical document.

4.3.1.3. Progression of COVID-19 by Day 29 (emergency room, hospitalisation for any duration or cause, death)

Progression of COVID-19 through Day 29 as defined by:

1. Visit to a hospital emergency room for management of illness
- OR
2. Hospitalization for acute management of illness for any duration and for any cause
- OR
3. Death

4.3.1.4. Proportion of Participants Who Progress to Develop Severe or Critical Respiratory COVID-19 at Day 8, 15, 22 and 29

Participants are defined as progressing to develop severe respiratory COVID-19 if they require supplemental oxygen either by nasal cannula, face mask, high-flow oxygen devices, or non-invasive ventilation.

Participants are defined as progression to critical respiratory COVID-19 if they require invasive mechanical ventilation or ECMO.

Participants who die prior to the timepoint of interest without first having received supplemental oxygen will be considered to have met the endpoint (composite estimand strategy).

Further detail on the severity of respiratory COVID-19 based on the proportion of participants meeting each tier of the Vir modified version of the NIAID Ordinal Scale for Clinical Improvement (Table 1) will be summarized.

Table 1 Ordinal Scale for Clinical Improvement

Ordinal Scale (Vir modified version, adapted from the Adaptive COVID-19 Treatment Trial [ACTT], 2020; referred to as National Institute of Allergy and Infectious Disease (NIAID) scale hereafter)
1) Not hospitalized, no limitations of activities
2) Not hospitalized, limitation of activities and/or requiring home oxygen ¹
3) Hospitalized, not requiring supplemental oxygen and no longer requiring ongoing medical care (used if hospitalization was extended for infection-control reasons)
4) Hospitalized, not requiring supplemental oxygen but requiring ongoing medical care (COVID-19-related or other medical conditions)
5) Hospitalized, requiring any supplemental oxygen
6) Hospitalized, requiring non-invasive ventilation or use of high-flow oxygen devices
7) Hospitalized, receiving invasive mechanical ventilation or ECMO ²
8) Death

¹ report as category 5 if using oxygen at home (unless were receiving home oxygen pre-morbidly), ² Participant in receipt of extracorporeal membrane oxygenation (ECMO) at the time of dosing on Day 1 are excluded from the study (participants who subsequently require ECMO may continue in the study).

